#### Acute and Habitual Dietary Intake

Participants will complete our adapted version of the Block Food Frequency Questionnaire (Block FFQ) which inquires about the frequency of consumption of 60 specific foods over the past 2 weeks (29) to measure habitual dietary intake. Food frequency questionnaires are the most practical and economical method for collecting dietary intake data in large studies (30). Block FFQ values correlated ( $r = .57$ ) with 4-day food record estimates for energy and most

nutrients (31). We have successfully used this version in previous studies (NORC5-34387, HHSN275201300015C) and published results.

#### Additional Surveys

We will administer the Short-Form International Physical Activity Questionnaire (IPAQ), which queries about physical activity over the previous days and has shown strong reliability ( $r = .80$ ; (32)). Participants will also complete a modified version of the Pittsburgh Sleep Quality Index, which will ask about sleep quality over the past week (33), which we can determine the previous night's sleep. Lastly, participants will complete the Edinburgh Handedness Inventory, which is a continuous measure of hand dominance (34).

fMRI scan paradigms. The participants will complete 2 types of functional MRI paradigms, a task-based paradigm and a resting-state paradigm.

The task-based paradigm will assess evoked blood oxygen level dependent (BOLD) response to receipt of study beverages (SSB and unsweetened) and a water solution, and logo-elicited anticipation of both SSB and unsweetened beverages and water solution. The paradigm is controlled by in-house scripts written in PsychoPy software. The visual stimuli are two beverage logos, a water logo, and a fixation cross. The logos served as branding for the beverages. Each logo (1 second) signals impending delivery of 3 mL of the associated beverage/water over 6 seconds, with the fixation cross otherwise presented. A jitter ranging from 5 to 13 ( $\bar{x} = 8$ ) seconds follows each trial. In total, the participants are presented 24 repeats of the events of interest over four 7-min runs. Each participant is exposed to the SSB and USB logos of their assigned flavor independent of their intervention assignment.

The resting-state scan will assess functional connectivity by examining the correlation of fluctuations of BOLD signals in different regions of the “resting” brain and will provide a measure of its functional organization. Resting-state fMRI data will be acquired in one run of 5 minutes; participants will be asked to remain still and relaxed and stay awake during the scanning.

#### **H. Study Intervention**

- During the 3-week (21 days) intervention period all participants will come to our lab at a consistent time Monday, Wednesday, and Friday to: 1) consume that day's beverage in lab; 2) complete hedonic ratings (described above); 3) pick up the following day(s) beverage; and 4) return the empty bottles from the previous day(s). On Fridays, participants will be given two bottles to take home and instructed to consume one per day.
- Empty bottles will be returned to increase compliance. In the case the participant is unable to attend an intervention assessment and cannot acquire their beverage, they will return the following day to resume. To remain in the study, the participants may not miss consuming the beverage for three consecutive days, and must consume the beverage >17 occasions.
- Following current protocols, the behavioral and scan sessions will be scheduled at approximately the same time in the day for each assessment (within-subject) and will occur after a 4-6 hour fast. Participants will be reminded of the day before and number of hours since last eaten will be recorded at assessment.
- During the intervention we will ask participants to consume their beverage 1 hour outside of a meal, as not to confound beverage with postprandial meal effects, and maintain their typical dietary patterns as to best mimic a real-world setting in which they elected to consume a new-to-market beverage daily.

## **I. Safety Management**

It is possible that the questionnaires may cause distress or embarrassment to the participants. One potential risk to participants is that it may be distressing to disclose information about psychiatric difficulties. In our estimation, there is a low risk of this possibility and the effects would probably be short-lived. We have conducted several thousand of these types of interviews with no adverse events. We will take steps to minimize this risk by informing them that their data will be confidential. Additionally, it is possible someone maybe embarrassed to be weighed. The research staff will be trained to be highly professional for the entire study visit. Data will be obtained from participants through surveys, taste assessments, height and weight measurements, fMRI scans, finger sticks, and saliva. There is a slight risk that these research records might be obtained by persons not authorized to do so. There is also a risk that participants may not understand the limits of confidentiality (i.e. that we will not keep certain information confidential, such as spontaneous disclosures on their part regarding suicidal ideation and child abuse [no measures inquire about sensitive topics such as these]). Data for all participants will be kept strictly confidential, except as mandated by law. All research files will be kept in locked file cabinets in a locked room in a locked building. Participants will be assigned a numerical code for identification in the files. Names and other identifiers will be kept in separate locked files and will never be recorded on any data forms. Statistical analyses will be performed on aggregate-level data; participants are never individually named. All entered data will be kept on the password protected, secured computers or networks at the research site. These data will be accessible only to research staff, using confidential usernames and passwords. All staff on this project will receive training in the ethical conduct of research with human participants prior to contact with data or research participants. Participants will be informed in detail about the limits of confidentiality, including disclosure of intentions to inflict harm to self or others and the possibility that we might break confidentiality to report suspected child or elder abuse. All participants will be told that participation is voluntary and that they may terminate their involvement at any time without any consequences. If, during any assessment, the project coordinator determines that a participant has developed a serious health problem, efforts will be made to help the participant access appropriate treatment as quickly as possible. In addition, any scans that suggest possible problems are sent to a radiologist for a consult. In the event of a potential problem, [name] will meet with the participant and the radiologist to discuss the findings, per protocol from the Biomedical Research Imaging Center.

## **J. Data Collection and Management**

All paper data will be stored in a locked filing cabinet in a locked room. All digital data will be stored on servers which require passwords to access. Data will be saved as confidential, coded files. All genetic data will be de-identified and will be kept in secure freezers until it is assayed.

Only authorized project staff will have access to the information gathered for this project. We will follow established data handling procedures as follows: (a) data will be reported in aggregate form only; (b) all data will be kept in locked file cabinets and/or in password-protected computer files; and (c) all personnel interacting with participants and having access to data are trained in confidentiality procedures.

Any paper documents will be stored in locked files, behind locked doors at the laboratory on campus at UNC-CH. The key that links participant names to the identification numbers will be kept separate from the data, also in a locked file.

fMRI data collected at the BRIC is sent over a secured server (PACS), this data is attached to coded numbers. fMRI data is accessed through this password protected server and transferred to the lab's protected databases. Unprotected personal information of subjects is never sent over the web.

#### **K. Recruitment Strategy**

Recruitment flyers will be placed on the UNC campus, in community centers, and restaurants in local Chapel Hill/Durham area. Additionally, we will use 'Join the Conquest', an online study listing and engagement site intended to improve transparency and awareness of research at UNC. Those interested in participating will be directed to fill a screening questionnaire, which will be used to determine participant eligibility. Eligible subjects will be contacted by research staff via the preferred method of the subject (phone, email, in person) to provide the consent for review and schedule the study assessments.

#### **L. Consent Process**

The consent will be emailed to the subject for review prior to enrollment. Study staff will be available to answer any questions prior to scheduling/meeting with subjects for the first assessment. Consent will be confirmed by trained research staff. Consent will be reviewed and confirmed and all answers regarding study expectations will be answered by trained staff on the pre-intervention behavioral visit.

## **Statistical Analysis Cover Page**

**Official Title: Neurobehavioral Plasticity to Regular Sugar-Sweetened Beverage Intake: An fMRI Experiment**

**NCT Number: NCT03490734**

**Document Date: January 25, 2023**

## **Statistical Analysis Plan**

### **A. Sample Size and Power**

Data collection was ended early due to COVID-19 (ending March 2020), resulting in a lower than anticipated sample size (160 vs. 230), which may impact results, specifically, measures of individual differences. As our sample was smaller than anticipated we performed a sensitivity analysis using Gpower (ver. 3.1.9.7, Heinrich Heine University Düsseldorf) for the primary hypothesis using alpha = 0.05, power of 0.80 and a total sample of 123 (accounting for missing data, incomplete data collection, etc.), and we are still able to detect effect of 0.25. Inclusion Criteria: Potential participants were eligible for the study if they had BMI scores between 18 and 34 at baseline. Exclusion Criteria: Individuals with probable current Axis I psychopathology or any fMRI contra-indicators (e.g., metal implants, braces) were excluded. Those with a probable Axis I diagnosis will be provided with treatment referral information and encouraged to seek treatment, current regular use (3 or more times a week) of psychoactive drugs (e.g., cocaine, marijuana, nicotine), regular smoking, serious medical problems (e.g., cancer, diabetes), dietary practices that do not allow for intake of intervention beverages.

### **B. Analysis Plan**

#### *1. Primary and Secondary Outcomes*

Behavioral data analysis (stop-signal reaction time & perceptual ratings of beverages): Continuous variables from the stop signal task and the visual analogue scale (VAS) ratings were summarized by descriptive statistics (e.g., mean, SD, range, median), examined via graphical analyses (e.g. histogram, Q-Q plot) and analyzed to assess the normality of the data. Data transformation of continuous variables were used as necessary. Model assumptions and potential outliers were analyzed with various modeling diagnostics and plotting techniques. Two analytic datasets are used. Participants that provided data at baseline and follow-up are used in a completers analysis (CA). An intent-to-treat (ITT) dataset, including all participants that were consented and completed one assessment, are also used. In that analysis, missing data are addressed via multiple imputation methods. Of note, in both the CA and ITT all subjects are included independent of their adherence to the intervention.

For **Aim 3**, reaction times from the stop signal task (SST) are analyzed. Following previous standards, reaction times <50 milliseconds are excluded (occurred prior to imputation). As we are not analyzing inhibition (inhibition accuracy/SSRT), no other exclusion criteria were used. Data from pre- and post-intervention SST measures are analyzed using PROC MIXED implemented in SAS (Version 9.4, Cary, NC). All available data from those completing the pre- and post-intervention behavioral visits (separate from the scan assessments) are used in the completers analysis. All those who consented are included in the ITT analysis with missing data imputed. Outcome variables assessed via the SST task are: mean reaction time, standard deviation, go accuracy of the assigned beverage (pre-/post-intervention). Each of the outcome variables is entered into 2x2 repeated measure mixed models, including group-by-time interactions. Control variables of no interest to be included are BMI, assigned flavor, and gender. Interactions are probed for pairwise comparisons using least-squared mean comparisons, specifically of a priori contrasts of interest: between-group baseline differences and follow-up differences, and within-assignment change from pre- to post-intervention. Bonferroni-adjusted two-tailed *p*-values less than 0.05 are considered significant.

For **Aim 4**, perceptual hedonic, taste and internal state ratings (assessed using visual analog scales (VAS)) are analyzed. Data from pre- and post-intervention perceptual ratings are

analyzed using PROC MIXED implemented in SAS (Version 9.4, Cary, NC). Pleasantness and Desire of the assigned beverage (pre-/post-intervention) are each entered into 2x2 repeated measure mixed models, including group-by-time interactions. Control variables of no interest to be included are BMI, assigned flavor, gender, and thirst. Four pairwise comparisons of interest (pre- and post-intervention differences by intervention assignment and within-assignment change over time) are probed. Tukey-adjusted two-tailed  $p$ -values less than 0.05 are considered significant.

**fMRI data preprocessing:** Neuroimaging data were preprocessed using the fMRIPrep pipeline. DICOMS were converted to the Brain Imaging Data Structure (BIDS file structure), then preprocessed using fMRIPrep. Prior to preprocessing, the first four volumes of each functional run were trimmed. fMRIPrep preprocessing included skull stripping using Advanced Normalization Tools (ANTs); tissue segmentation using FSL's Automated Segmentation Tool (FAST); and spatial normalization to Montreal Neurological Institute (MNI) 152-Asymmetrical space using ANTs' registration option. Functional data were co-registered to anatomical data using FSL's FMRIB's Linear Image Registration Tool (FLIRT) with boundary-based registration. Functional data were additionally motion corrected using FSL's MCFLIRT and corrected for fieldmap distortion. In FSL, final preprocessing included spatial smoothing using a 5mm full width half maximum isotropic Gaussian kernel, high-pass filtering, adding temporal derivatives, adjusting for autocorrelation, and adjusting for nuisance regressors, including the 6 motion parameters, 6 anatomical component-based noise correction regressors (aCompCor), and high motion time points (FD>0.5mm). A functional run for a subject was excluded if >30% of total volumes were flagged as high motion points.

**fMRI primary analyses:** Neuroimaging analyses were primarily completed in FSL (FMRIB Software Library, [www.fmrib.ox.ac.uk/fsl](http://www.fmrib.ox.ac.uk/fsl)). Individual (level 1), within-subject (level 2), and group level (level 3) analyses were carried out in FSL's fMRI Expert Analysis Tool (FEAT). At the 1st (individual) level, SSB, USB, SSB logo, USB logo vs. water logo contrasts were created. These were carried forward to a within-subject (level 2) model testing for the effect of time.

At the 2nd (within-subject) level analyses, the above SSB, USB, SSB logo, USB logo vs. water logo data were put into a within-subject t-test testing individual-level differences as a function of time, i.e., post-intervention > pre-intervention (testing for increases in BOLD response as a function of the intervention) and pre-intervention > post-intervention (testing for decreases in BOLD response as a function of the intervention).

Level 3 (group-level) analysis used the resulting level 2 data (post- > pre-intervention; SSB/USB > water taste/logo to test for increases in response and, separately, pre- > post-intervention; SSB/USB > water taste/logo for decreases in response) to test for the main effect of the intervention and the interaction of BMI (**Aims 1 and 2**).

- a. First, the assignment\*BMI interaction (**Aim 2**) is tested with flavor assignment, gender, thirst, and beverage pleasantness as covariates of no interest. By using the level 2 within-subject data that tested for the effect of time, this results in a time\*group\*BMI interaction. Contrasts of interest for the group model are SSB > water and SSB logo > water logo. This is tested with the pre- > post-intervention and the post- > pre-intervention level 2 data. Parameter estimates of significant BOLD response are plotted for visualization purposes.
- b. **Aim 1** is tested in a separate model controlling for BMI (no interaction), flavor assignment, gender, thirst, and beverage pleasantness. Contrasts of interest for the group model are SSB > water and SSB logo > water logo. This is tested with the pre- > post-intervention and the post- > pre-intervention level 2 data. Mean

cluster parameter estimates of significant BOLD response are plotted for visualization purposes.

All group-level analyses were corrected for multiple comparisons by using the threshold free cluster enhancement (TFCE), nonparametric thresholding algorithm in FSL's RANDOMISE (n permutations = 10000), resulting in a family-wise error rate corrected significance threshold of  $p_{FWE} < 0.05$ . At the group level, functional data were masked via an inclusive grey matter mask to reduce the number multiple comparisons, resulting in whole brain, grey matter analyses. The mask was created via the ICBM 2009c Nonlinear Asymmetric template that was binarized at a threshold of 0.04 using FSLmaths. Localization of significant clusters will be used and determined using Mango's MNI atlas tool.

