### **B. Study Objectives**

**Aim 1:** Test the neurobehavioral adaptions in response to repeated intake of branded SSBs relative to unsweetened, flavored control beverages (USB).

*We hypothesize that daily SSB intake will lead to:*

- a. *increases in parietal/occipital brain response during exposure to the SSB brand;*
- b. *decreased dorsal prefrontal and hippocampal response to the SSB brand;*
- c. *reduced striatal response during receipt of the assigned SSB,*

*relative to baseline and to those who are assigned to consumed the control beverage.*

**Aim 2:** Test whether BMI mediates the neurobehavioral response patterns to the consumed beverages as a function of daily SSB intake relative to baseline and to those who are assigned to consume USB.

*We hypothesize that there will be no significant interaction, such that those individuals with elevated BMI will show no difference than those at a lower BMI in the brain adaptions described in Aim 1.*

**Aim 3:** Test the impact of repeated consumption of SSBs on behavioral responses (reaction time and response inhibition) to the beverage brands measured by the stop sign task (SST).

*We hypothesize that mean reaction time to Go trials will result in a significant interaction of group assignment (sugar vs. control) by pre-/post- daily consumption. Specifically, we hypothesize that the sugar group will show a decreased reaction time to Go trials, representing faster responses relative to the control group and baseline.*

**Aim 4:** Test the impact of repeated consumption of sugar-sweetened beverage on perceptual hedonic and taste ratings.

*We hypothesize that daily beverage intake will lead to:*

- a. *no change in pleasantness and desire ratings as a function of repeated consumption of the assigned beverages.*
- b. *an assignment (sugar vs. control) by time (pre-/post- daily consumption) interaction for desire ratings of the non-assigned beverages. Specifically, we hypothesize that there will be a decrease in desire ratings of the control beverage after having consumed a SSB daily. We expect no change in pleasantness.*

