was presented and the other three runs presented the logo of the unassigned beverage (of the same flavor). The order of assigned vs. unassigned was randomized across the sample. Within each run of this task, 64 (20 “go”) trials were presented, and participants were instructed to make a speeded response to a “go” stimulus except trials when an additional “stop” signal occurs (an X presented over the logo), in which case participants were instructed to withhold their response. The beverage logos (used as the “go” stimuli) were presented in two colors, indicating that the participant was to press the right or left of the screen. This speeded reaction time establishes a prepotency to respond to the logos. There were also trials where the “go” stimulus was followed, after a variable delay, by the stop-signal where the participants were instructed to withhold their response. The onset of the stop-signal, or stop-signal delay (SSD), varied and depended on the participant’s performance, such that it is decreased after a previous failure to inhibit and increased after a previous inhibition (resulting in SSD staircases across the course of the task). Participants were instructed to react quickly but also inhibit responses on trials where the stop-signal appeared as correctly responding and inhibiting were equally important.

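### Aim 3 mean RT is not restricted to correct-side Go responses, and no rule ties it to the go-accuracy and RT-SD results

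*SAP*

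**What the plan says.** Protocol section B, Aim 3, states: "We hypothesize that mean reaction time to Go trials will result in a significant interaction of group assignment" by time. A drop in the sugar group is to be read as faster responding than in the control group and than at baseline. The endpoint is limited to Go trials, but not to correct ones.

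Protocol section G describes a two-choice task. The logos were "presented in two colors, indicating that the participant was to press the right or left of the screen", so a wrong-side press is possible.

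SAP section B.1 gives one rule for these data, "reaction times <50 milliseconds are excluded (occurred prior to imputation", followed directly by "As we are not analyzing inhibition (inhibition accuracy/SSRT), no other exclusion criteria were used". The outcomes are "mean reaction time, standard deviation, go accuracy of the assigned beverage (pre-/post-intervention". On modelling it says: "Each of the outcome variables is entered into 2x2 repeated measure mixed models, including group-by-time interactions". The planned contrasts include the change from pre to post within each arm. For behavioural data in general the SAP adds "Model assumptions and potential outliers were analyzed with various modeling diagnostics and plotting techniques", with no threshold and no action.

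Neither document restricts mean RT to correct-side responses, sets an upper RT limit, or says how omitted responses are handled. Neither says how an RT result is to be read if accuracy or RT SD also changes.

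**The concern.** The reason given does not support the rule. Leaving out inhibition and SSRT may remove the need for the validity checks that belong to those measures. It has no bearing on whether a Go RT measures speed. In a left/right task, a wrong-side press is not a fast correct reaction to the logo, and one very slow response can weigh heavily in a mean over a limited number of trials.

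A mean over all responses therefore mixes three things: speed of correct responding, the share of errors, and the share of slow responses. If the sugar arm made relatively more quick errors after 21 days, or relatively fewer slow responses, its mean RT would fall with no change in correct-response speed. That fall is in the direction Aim 3 predicts. The group-by-time test is affected only if the change differs between arms. The within-arm pre/post contrasts are affected even when it does not, and the Aim 3 hypothesis includes a comparison with baseline.

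**Working it through.** **1. The plan's own figure.** SAP section A states a detectable effect of 0.25 at alpha 0.05, power 0.80 and N = 123, without naming the metric or the test. A noncentral F with 1 numerator df, two groups and noncentrality f² × 123 gives f = 0.2546, and power 0.785 at f = 0.25. The figure is reproduced to rounding. It is stated for the primary hypothesis. The number analysed for Aim 3 is not given, and the point here does not depend on it.

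**2. Detectable difference in RT change.** For two equal groups with N = 123, a two-sided 0.05 test has power 0.80 at d = 0.509 (about 2 × 0.2546). In milliseconds this is 0.509 × SD of change. The documents give no SD of change, so I assume 30 to 60 ms:
- SD 30: 0.509 × 30 = 15.3 ms
- SD 60: 0.509 × 60 = 30.6 ms

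**3. Shift from a change in error share.** Mean RT = (1 − p) × RT_correct + p × RT_error. With both component means fixed, the shift = Δp × (RT_error − RT_correct). The gap and Δp are assumptions.

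| Errors faster by | +1 point | +5 points | +10 points |
|---|---|---|---|
| 50 ms | −0.5 ms | −2.5 ms | −5 ms |
| 100 ms | −1 ms | −5 ms | −10 ms |
| 150 ms | −1.5 ms | −7.5 ms | −15 ms |
| 200 ms | −2 ms | −10 ms | −20 ms |

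**4. Shift from slow responses.** Section G gives three assigned-logo runs of 64 trials, 20 of them Go as written, so 3 × 20 = 60 Go trials per visit. If 20 were instead the stop count, there would be 3 × 44 = 132. One fewer response that is 300 to 1,500 ms slower than usual (assumed) moves the mean by 300/60 to 1,500/60 = 5 to 25 ms, or by 300/132 to 1,500/132 = 2.3 to 11.4 ms. Only slow responses count here, because an omitted response has no RT.

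**5. Chance that such a shift alone is significant.** Suppose it occurs in one arm only, with no true change in correct-Go RT. With 61.5 per arm and unadjusted two-sided 0.05, the chance is Φ(shift / (SD × √(2/61.5)) − 1.96), where √(2/61.5) = 0.180.

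| Shift | SD of change 60 | SD of change 30 |
|---|---|---|
| 5 ms | 7% | 15% |
| 10 ms | 15% | 46% |
| 20 ms | 46% | 96% |

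Bonferroni adjustment would lower these figures.

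**6. Within-arm contrasts.** The standard error of one arm's mean change is about SD/√61.5 = 3.8 to 7.7 ms, against 0.180 × SD = 5.4 to 10.8 ms for the between-arm difference. The within-arm contrasts are therefore more sensitive to a given shift, and a change common to both arms does not cancel in them.

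**The case against.** Several stronger readings are tempting and are not supported.

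- *A reader might infer that a change in errors would pass unnoticed as faster responding.* Go accuracy and RT SD have their own group-by-time tests in the same paragraph. For a one-arm rise of 5 points with a 150 ms gap (7.5 ms), the formula in step 5 of the working gives the RT test a 10% to 28% chance of significance. With an assumed SD of accuracy change of 7 to 11 points, the accuracy test has a 71% to 98% chance. This largely stands. What remains is that nothing links the two results, that a non-significant accuracy test does not show the RT to be clean, and that slow but correct responses leave accuracy unchanged.
- *A reader might infer that the SAP is known to have kept wrong-side responses.* That is the natural reading of a sentence placed directly after a trial-level rule. It could instead mean criteria for whole participants or runs, and the task software's definition of mean RT is not given.
- *A reader might infer that failed-stop responses enter the mean.* The SAP omits the word Go from this outcome, but the protocol limits the endpoint to Go trials. A sentence saying so is enough.
- *A reader might infer a large loss of precision.* Simulation with correct RT 450 ms (SD 100) and 1% of responses near 1.5 s raises the SD of one person's mean from 12.8 to 19.2 ms at 60 trials and from 8.6 to 12.9 ms at 132, about 2.2-fold in sampling variance. That is within-person variance. The variance of the tested change rises by 2 × (19.2² − 12.8²) = 410 ms² or 2 × (12.9² − 8.6²) = 185 ms². An SD of change of 30 to 60 ms then grows by about 6% to 21% or 3% to 10%. All of this also assumes a response window of at least 1.5 s, which the protocol does not give.

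It is also fair to object that collection ended in March 2020 and that the SAP of January 2023 reports the 50 ms rule as already applied. Replacing the endpoint now would be a post hoc redefinition. That stands and shapes the fix.

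**Conclusion.** The point holds in a limited form and is worth acting on. The stated reason for having no further rule does not justify leaving wrong-side and very slow responses in a two-choice Go RT that is to be read as speed. Restricting to correct-side Go responses is a better and cheap definition. The documents do not show that the group-by-time result is biased; that needs the change in errors or slow responses to differ between arms.

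Under the assumed inputs, the error route moves mean RT by 0.5 to 20 ms against a detectable difference of about 15 to 31 ms. It is small in most of that range and material only near the top, at about a 10-point change in error share. Slow responses can matter at smaller counts. The gaps, the changes in trial share, the SD of change and the use of N = 123 for Aim 3 are assumptions. The absence of a correct-side rule, an upper limit and an interpretive link is read from the text.

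**What to change.** - Compute Aim 3 mean RT and RT SD on correct-side Go trials only, before imputation. State explicitly that responses on stop trials are excluded and that omitted responses contribute no RT.
- Report this beside the existing 50 ms-only rule and label it as specified after data collection. If the task software already uses correct Go trials only, one sentence saying so closes this part.
- Add one sensitivity analysis with a single upper RT limit fixed blind to arm. A multiple of each person's own SD is less suitable, because slow responses inflate that SD. Any upper limit also truncates what the RT-SD outcome measures, so it belongs in a sensitivity analysis.
- State that any RT effect is interpreted jointly with the go-accuracy and RT-SD results.

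The cost is re-deriving two variables, provided trial-level data were stored, and some SAP wording. The downsides are slightly fewer trials per person and a definition added after data collection.
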